16.62 Conversion to Mastectomy

The conversion rate to mastectomy secondary to persistent positive margins; poor cosmesis within the first year of attempting BCS; or inability to satisfy the radiation dose constraints on the boost to the lumpectomy bed of each site of disease

All eligible patients who have initiated surgery will be included in the analysis of conversion to mastectomy. A 95 % binomial confidence interval will be constructed for the percentage of patients who converted to mastectomy. Logistic regression analysis will be used to assess whether the likelihood of conversion to mastectomy differed with respect to patient and/or disease characteristics.

An interim efficacy analysis will not be performed; final analysis will be performed at year 7 after patients have at least 5 years of follow-up.

Patients enrolled subsequent to surgery will be excluded from this analysis.

16.63 Analysis of Patients With Margins <2mm

A subset analysis will be done of patients with close margins (< 2 mm) who did not undergo re-excision.

The purpose is to see whether the inclusion of these patients inflated the local recurrence (LR) rate. In addition, the LR rate of patients with close margins (< 2 mm) who did not undergo re-excision will be estimated with point estimate and 95% confidence interval.

16.64 Adverse Events

The NCI CTCAE version 4.0 will be used to assess the type and severity of adverse effects of breast conserving surgery for women multiple ipsilateral primary breast cancer as well as the type and severity of radiation-related adverse effects of whole breast radiation with a boost to 1 large or > 1 lumpectomy site in women multiple ipsilateral primary breast cancer. However, CTCAE version 5.0 will be used for expedited adverse event reporting.

16.65 Incidence of Breast Lymphedema (BLE)

For each time point, a 95 % binomial confidence interval for the proportion of patients diagnosed with breast lymphedema will be determined. Breast lymphedema will be defined as a patient who has a symptom survey score > 0 and presence of breast edema by physical examination.

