Patients undergoing lumpectomy for MIBC and breast radiation with boost to both tumor beds are hypothetically at increased risk of BLE. We will evaluate the incidence of BLE and symptoms as diagnosed using clinical examination along with the same questionnaire used in the previous study to see if BLE is more common in women treated with BCT for MIBC than reported in our previous BLE study evaluating patients undergoing lumpectomy and radiation for unifocal breast cancer.

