2.24 Incidence of Breast Lymphedema

To assess incidence of breast lymphedema.

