7.4 Cosmesis

Following surgery, patients will complete questionnaire booklets at the following time points: 5 to 30 days following final surgery (initial post-operative visit); every six months (\pm 1 month) for the first 2 years following completion of WBI; then yearly (\pm 2 months) for the next 3 years following completion of WBI to assess cosmetic outcome. The

patient's surgeon will complete the surgeon questionnaire 5 to 30 days following final surgery (initial post-operative visit) to assess cosmetic outcome. Patients registered after surgery will still complete the questionnaire at the timepoints feasible, based on the timing of their registration.

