7.7 Patient Follow-up After Completion of WBI

All eligible patients will enter the observation phase of this trial after completion of WBI (see test schedule, Section 4.0). At the follow-up visits, patients will complete a symptom survey and undergo a physical examination. The breast lymphedema symptom survey will assess breast heaviness, swelling, redness, and discomfort. The physical examination will assess the presence or absence of breast edema, which will combine with the symptom score to define cases of breast lymphedema. Lymphedema should be graded using CTCAE version 4.0 (see Section 10.51).

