12.2 Time of Registration: Pre-surgery vs Post-surgery

13.0 Treatment/Follow-up Decision at Evaluation of Patient

13.1 Follow-Up After Completion of WBI

Patients will be followed as per the test schedule for 5 years after completion of WBI.

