Breast Lymphedema (BLE) Symptom Survey
(Degnim *et al.* 2008)

Alliance Number: _____ Patient Initials (last, first) _____ Date: _____

Please answer the following questions regarding current (within the last week) symptoms in the operated breast.

1. Does your breast appear or feel swollen?

Not at all 0 1 2 3 4 5 6 7 8 9 10 A lot

2. Does your breast feel heavy?

Not at all 0 1 2 3 4 5 6 7 8 9 10 A lot

3. Is your breast redder in color?

Not at all 0 1 2 3 4 5 6 7 8 9 10 A lot

4. Do you have pain, tenderness, or discomfort in your breast?

Not at all 0 1 2 3 4 5 6 7 8 9 10 A lot

5. Do you have armpit fullness or numbness?

Not at all 0 1 2 3 4 5 6 7 8 9 10 A lot

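### Section 16.65 estimates the prevalence of breast lymphedema at each visit, whereas goal 2.24 asks for its incidence; add the cumulative incidence of first breast lymphedema.

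*Combined protocol and SAP*

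**What the plan says.** Goal 2.24 reads: "To assess incidence of breast lymphedema". Goal 2.23 and the title of section 16.65 use the same term. The rationale in section 1.243 says "We will evaluate the incidence of BLE and symptoms as diagnosed using clinical examination", and adds that the aim is to see whether BLE is more common after breast conservation for multiple ipsilateral cancers than in the group's previous study of unifocal cancer.

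The analysis in section 16.65 is one sentence: "For each time point, a 95 % binomial confidence interval for the proportion of patients diagnosed with breast lymphedema will be determined". The case definition follows: "Breast lymphedema will be defined as a patient who has a symptom survey score > 0 and presence of breast edema by physical examination". Section 7.7 describes how the two parts are collected after WBI: "The physical examination will assess the presence or absence of breast edema, which will combine with the symptom score to define cases of breast lymphedema". The symptom survey in Appendix IV instructs: "Please answer the following questions regarding current (within the last week) symptoms in the operated breast".

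Under section 7.4 the booklet containing this survey is given once soon after final surgery, then every six months for two years after WBI and yearly for three more. Table 4.2 (footnote 4) schedules only the post-WBI booklets for women registered after surgery.

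**The concern.** Incidence counts women who develop a condition over a period. The planned statistic counts women who have it on a given day. A woman who meets the definition at 6 months and not at 12 months enters the first proportion and not the second, and no planned statistic counts her once as a woman who developed BLE.

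The denominators also change. Sections 16.61, 16.62 and 16.66 each name an analysis population; section 16.65 names none. Under section 13.4, women with a recurrence, or who refuse further study tests, move to event monitoring, where only disease and vital status are collected. They therefore leave the later BLE proportions. Women registered after surgery have no scheduled post-operative survey. Successive proportions thus describe different groups.

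What is at stake is goal 2.24 and the question in section 1.243. A series of up to eight visit proportions does not give one figure for how many women were affected.

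**Working it through.** **Is the planned figure a prevalence?** Three elements settle it. The survey asks about the last week (Appendix IV). The examination records edema as present or absent at the visit (7.7). The definition joins the two (16.65), and no rule carries an earlier diagnosis forward.

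**Does another section supply an incidence?** Section 16.64 covers type and severity by CTCAE. Lymphedema is graded at baseline and at each evaluation (10.51), but that is a different definition, and no worst-grade or ever-affected summary is stated. Section 16.662 uses BLE only as a covariate. No time-to-first-BLE or ever-affected analysis appears anywhere.

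**Is there a BLE figure to reproduce?** No. The documents give no expected rate, precision or sample size for BLE. The only stated figure for this type of interval is in section 16.51, a lower bound of 25.7% for 35 of 100. The exact (Clopper-Pearson) bound is 25.73%, which agrees.

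**Direction.** With a common denominator, the women affected at visit k are a subset of those affected at any visit up to k. Prevalence at k is therefore at most the proportion ever affected by k. The two are equal only if every case so far is still present at k.

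**Size (illustration).**

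Inputs:
- Survey visits after WBI, from section 7.4: 6, 12, 18 and 24 months (K = 4), then 36, 48 and 60 months (K = 7). The post-operative visit is left out because ordinary surgical swelling may meet the definition and because women registered after surgery have no such scheduled survey.
- Visit prevalence p, assumed constant: 10%, with 20% as a second case.
- Persistence r, the assumed chance that a case at one visit is still a case at the next: 100% down to 50%.
- No dropout.

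The chance of becoming a case between visits that keeps prevalence constant is

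e = p(1 − r)/(1 − p),

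and the proportion ever affected over K visits is

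1 − (1 − p)(1 − e)^(K − 1).

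For p = 0.10 and r = 0.80: e = 0.10 × 0.20/0.90 = 0.0222. By 24 months, 1 − 0.90 × 0.9778³ = 15.9%. By 60 months, 1 − 0.90 × 0.9778⁶ = 21.4%.

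For p = 0.10 and r = 0.50: e = 0.10 × 0.50/0.90 = 0.0556. By 24 months, 1 − 0.90 × 0.9444³ = 24.2%. By 60 months, 1 − 0.90 × 0.9444⁶ = 36.1%.

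| Visit prevalence | Persistence | Ever affected by 24 months | Ever affected by 60 months |
|---|---|---|---|
| 10% | 100% | 10.0% | 10.0% |
| 10% | 90% | 13.0% | 15.8% |
| 10% | 80% | 15.9% | 21.4% |
| 10% | 50% | 24.2% | 36.1% |
| 20% | 100% | 20.0% | 20.0% |
| 20% | 90% | 25.9% | 31.3% |
| 20% | 80% | 31.4% | 41.2% |
| 20% | 50% | 46.4% | 64.1% |

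Counting the post-operative visit as well (K = 5 and K = 8) raises the 10% rows for 80% and 50% persistence to 17.7-28.4% by 24 months and 23.1-39.7% by 60 months.

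The model applies one persistence value to both six-monthly and yearly gaps and holds prevalence flat. It shows the order of the gap and does not predict it.

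**The case against.** The strongest objection is that nothing in the documents says BLE resolves. Section 1.243 describes signs and symptom scores, not their course over time. If BLE is permanent once present and follow-up is complete, prevalence at the last visit equals cumulative incidence. If cases cluster early, the peak visit lies close to the ever-affected figure. This stands, and it is why the gap is stated from zero upward.

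A reader might infer that BLE comes and goes and that the plan will therefore make a common morbidity look uncommon. The documents support neither part. They give no persistence, and no expected BLE rate for this trial. Nor does the plan report one low figure: it reports a series of proportions, each with its interval, and these are valid description. Selective dropout could also move a visit proportion in either direction.

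The word for diagnosed in section 16.65 might be read as diagnosed by that time. The one-week recall, the visit-based examination and the absence of a carry-forward rule point the other way.

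It can fairly be said that BLE is a goal but is not in the list of secondary endpoints in section 16.2, and that no hypothesis, sample size or stopping rule depends on it. That limits the importance of the point. It does not remove the mismatch.

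**Conclusion.** The point holds in a limited form. The goal and the section title ask for incidence, and the stated method yields point prevalence. Followed as written, the plan leaves goal 2.24 unanswered if any case resolves between visits.

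The direction needs only a common denominator. The size rests wholly on assumed prevalence and persistence. At 10% per visit it runs from no gap to about 6-14 percentage points by 24 months and 11-26 points by 60 months, for persistence of 80% down to 50%. A claim that the plan certainly understates BLE, or by a known amount, goes beyond what the documents show. The primary endpoint and the sample size are unaffected.

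**What to change.** In section 16.65:

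1. Keep the per-visit proportions, label them prevalence and state the denominator of each, including how missed visits are treated.
2. Add the cumulative incidence of first BLE, with a 95% confidence interval, at 24 and 60 months after WBI. Count from the 6-month post-WBI visit, so that women registered before and after surgery share the same assessments. Treat death, recurrence leading to event monitoring (13.4) and mastectomy as competing events. Section 16.61 already uses a competing-risk framework for the primary endpoint.
3. Add two sensitivity analyses. One includes the post-operative visit (5 to 30 days after final surgery) for women registered before surgery. The other requires BLE at two consecutive visits, because any score above 0 with edema qualifies and isolated borderline positives can accumulate over seven visits.

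The cost is a change to the analysis text; no new visit or form is needed. Two limits should be stated with the result. Onset is known only to within 6- or 12-month intervals. The baseline booklet (Appendix II) contains only the two LASA items, and only CTCAE lymphedema is graded at baseline, so BLE symptoms already present before surgery cannot be excluded.

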In this study, we will use the independent scales for satisfaction with breasts and satisfaction with overall outcome from the Breast Q[©] BCT module. Although the final version of the BCT module is still being finalized, the individual questions will not change and no questions will be added, therefore using these questions will enable calculation of a score once the Breast Q[©] BCT scoring is complete.

1.243 Breast Lymphedema (BLE) Symptom Survey (Degnim *et al.*, 2008).

Lymphedema in the ipsilateral arm is a well-recognized complication following breast/axillary surgery, but can also occur in the breast after surgery. We have previously evaluated clinical and surgical factors associated with the development of postoperative breast lymphedema (BLE); yet, BLE diagnosis is currently non-standardized and is based on clinical impression.

Previously, we prospectively evaluated patients undergoing non-mastectomy procedures for signs and symptoms of lymphedema in the operated breast. BLE diagnosis was based on a graded physical exam targeting clinical signs of diffuse skin edema, erythema, and their location. Diagnosis was independent of patient reported symptoms. Additionally, patients also rated symptoms in their operated breast for heaviness, discomfort, redness, visible swelling and associated degree of distress using a 10-point scale (“not at all” = 0 to “a lot” = 10). In subjects with clinical BLE, skin edema and breast erythema were observed in 26/26 (100 %) and 13/26 (50 %), respectively, compared to 5/38 (13 %) and 4/38 (11 %) without clinical BLE, respectively. BLE was observed in more than one quadrant for the majority of patients with BLE (skin edema 18/26 = 69 %, and erythema 10/13 = 77 %). Additionally, BLE patients had significantly higher scores for breast heaviness, discomfort, redness, and swelling and distress associated with these symptoms was significantly elevated only for symptoms of breast heaviness (mean 3.4 vs. 1.0, $p = 0.01$) and discomfort (mean 2.9 vs. 1.4, $p = 0.03$).

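### The trial's case definition of breast lymphedema requires symptoms plus edema, but the earlier study it is to be compared with diagnosed by graded examination alone, so the descriptive comparison mixes two definitions with a bias of unknown sign

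*Combined protocol and SAP*

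**What the plan says.** Section 16.65 defines a BLE case by two conditions that must both hold: "symptom survey score > 0 and presence of breast edema by physical examination". For each time point it plans a 95% binomial confidence interval for the proportion of cases. Section 7.7 has the same structure: the examination records whether breast edema is present, "which will combine with the symptom score to define cases of breast lymphedema".

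Section 1.243 describes the earlier study differently. There, "BLE diagnosis was based on a graded physical exam targeting clinical signs of diffuse skin edema, erythema, and their location". It adds: "Diagnosis was independent of patient reported symptoms". Symptoms were rated in that study but did not decide who was a case.

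Section 1.243 then states the aim of the present evaluation: "to see if BLE is more common in women treated with BCT for MIBC than reported in our previous BLE study". It says BLE and symptoms will be assessed "as diagnosed using clinical examination along with the same questionnaire used in the previous study".

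The plan describes the symptom survey in two ways. Section 7.7 says: "The breast lymphedema symptom survey will assess breast heaviness, swelling, redness, and discomfort". The survey printed in Appendix IV has five items, each scored 0 to 10, and the fifth asks: "Do you have armpit fullness or numbness". No scoring rule says which items count towards the score.

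**The concern.** A woman with edema on examination and a symptom score of zero could be a case in the earlier study and cannot be one here. A woman with slight edema and a single symptom point could be a case here and may not have met the earlier graded diagnosis. A difference between the two rates, or the lack of one, could then come from the definitions and not from treating more than one site with lumpectomy and boost.

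The stake is a stated background question: whether multi-site breast conservation carries more breast lymphedema. Section 16.65 plans no examination-only rate and does not mention the difference in definitions. If it is followed as written, the only rate available for the comparison is the composite.

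**Working it through.** **Inputs from Section 1.243 (earlier study)**
- With clinical BLE: skin edema 26/26, erythema 13/26.
- Without clinical BLE: skin edema 5/38, erythema 4/38.

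**Reproducing the stated percentages.** 26/26 = 100%, 13/26 = 50%, 5/38 = 13.2%, 4/38 = 10.5%. All agree with the rounded figures in the text.

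**Inferred denominator.** 26 + 38 = 64. The documents give neither this total nor an incidence for the earlier study, so what follows is illustration.
- Diagnosed by graded examination: 26/64 = 40.6% (exact 95% CI 28.5% to 53.6%).
- Any skin edema on examination: (26 + 5)/64 = 31/64 = 48.4% (exact 95% CI 35.8% to 61.3%).

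**The examination criteria differ as well as the symptom rule.** All 26 diagnosed women had skin edema, but so did 5 women who were not diagnosed. Edema was therefore not sufficient for the earlier diagnosis. Sections 7.7 and 16.65 ask only whether breast edema is present.

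**Applying the trial's rule to the 64 women.** Let s be the share of edema-positive women whose symptom score is zero. The documents do not give s; a range of 0 to 40% is assumed. If presence of edema means any edema:

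rate = (31/64) × (1 − s)

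If instead the examination criterion were identical in both studies:

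rate = (26/64) × (1 − s)

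| s (assumed) | Any edema plus symptoms | Difference from 40.6% (points) | Same examination plus symptoms |
|---|---|---|---|
| 0% | 48.4% | +7.8 | 40.6% |
| 5% | 46.0% | +5.4 | 38.6% |
| 10% | 43.6% | +3.0 | 36.6% |
| 16.1% | 40.6% | 0 | 34.1% |
| 20% | 38.8% | −1.9 | 32.5% |
| 30% | 33.9% | −6.7 | 28.4% |
| 40% | 29.1% | −11.6 | 24.4% |

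Break-even is where 31 × (1 − s) = 26, so s = 5/31 = 16.1%. Below that share the trial's rule reads higher than the earlier diagnosis in the same women; above it, lower. The last column shows a pure downward shift, but only by assuming identical examination criteria.

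**The armpit item.** Both conditions are required, so the fifth item changes a woman's status only if she has edema on examination, scores zero on all four breast items, and scores above zero on the armpit item. The documents do not say how many women that would be.

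**The case against.** The strongest case against acting has four parts.

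- **The comparison is informal.** It appears as one statement in the background. Goal 2.24 asks only for the incidence, Section 16.2 does not list BLE among the secondary endpoints, and Section 16.65 plans intervals with no test or benchmark. This stands, and it limits the weight of the point. It does not remove the mismatch, because Section 1.243 still says the comparison will be made.
- **The symptom requirement may lose few women.** If the score is a simple total, a single point on any item passes the threshold, and Section 1.243 reports significantly higher scores in women with BLE for all four breast symptoms. This also stands: s may be small. But at small s the looser examination criterion dominates and pushes the rate up, so a small s does not make the definitions agree.
- **The earlier study is imprecise.** An interval of 28.5% to 53.6% around 26/64 is wider than most of the shifts in the table. That is correct, but it argues for caution with the comparison as a whole and not for leaving the definitions unmatched.
- **The data are already separate.** Examination and survey are recorded individually, so an examination-only rate can be derived at any time. That is true, and it is why the remedy is cheap. The plan does not yet say that this rate will be reported or used.

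A reader might go further and infer that the composite must understate BLE and so hide a real excess. The documents do not support that. It needs the same examination criterion in both studies, and the 5/38 figure indicates that the criteria may differ. A reader might also treat 31/64 as a strictly matched comparator. That is not shown either: it counts five women whom the earlier study classed as non-cases, and nothing establishes that the two studies record edema in the same way.

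**Conclusion.** The mismatch is in the text. Sections 16.65 and 7.7 require symptoms together with edema, whereas the earlier study in Section 1.243 diagnosed by graded examination independently of symptoms. The planned descriptive comparison therefore uses two case definitions, with a bias of unknown sign. On the inferred 64 women and an assumed s of 0 to 40%, the trial's rule gives 48.4% to 29.1% against 40.6%. That is about +8 to −12 percentage points, with the sign changing at s = 16.1%. These figures rest on three assumptions: the inferred denominator, the assumed range for s, and presence of edema meaning any edema.

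The difference between four symptoms in Section 7.7 and five items in Appendix IV is real but minor. The point bears on a secondary descriptive aim. The primary endpoint and the conduct of the trial are unaffected.

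**What to change.** In Section 16.65:

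1. Keep the composite definition. At each time point also report the examination-only breast edema rate with its 95% binomial confidence interval.
2. Use the examination-only rate, not the composite, for any comparison with the earlier study. Show it beside both earlier figures: 26/64 by graded diagnosis and 31/64 with any skin edema.
3. State that the examination criteria may still differ unless the earlier grading rule is applied in this trial. Dropping the symptom requirement does not by itself make the rates comparable.
4. State which survey items enter the symptom score, and reconcile Section 7.7 with Appendix IV. A sensitivity version using the four breast items is enough. Leaving out the armpit item can only keep the composite the same or lower it, so that version should be labelled as a sensitivity analysis.

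The cost is one extra row per table, the small four-item sensitivity version, and a few sentences on scoring and comparability. The examination and the survey are already collected, so no data collection changes. Applying the earlier grading rule would be a further step, and the fix does not depend on it.
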